- b. **Inclusion/Exclusion Criteria:** All patients over the age of 18 who are receiving hemodialysis for ESRD are eligible to participate in the initial survey. Patients will be excluded if they are under the age of 18, or unable to consent for other reasons (i.e. dementia). Only transplant eligible patients may participate in the COACH intervention. Patients who have not been referred for kidney transplantation will be evaluated for transplant eligibility via chart review by a study transplant nephrologist for transplant candidacy. If the patient is eligible for transplant but not referred, the transplant nephrologist will discuss with the primary nephrologist if the participant is an appropriate candidate and reasons they have not been referred. We will defer the transplant referral to the attending nephrologist. Our major exclusion criteria are nursing home resident, >79 years of age, active or recent malignancy, inoperable coronary artery disease, or comorbid illness that will make it unlikely that the patient will survive >3 years after transplant.
- c. **Study Timelines:** The proposed research combines both a longitudinal observational cohort study to examine the structure of HD clinic social networks and a targeted transplant education intervention (COACH) trial to test the role of the network in the dissemination of knowledge, attitude, and behaviors with the overall goal of improving access to kidney transplantation. Data will be analyzed yearly and modifications and interventions will be made accordingly.
- d. **Study Procedure and Data Analysis:**
 - i. After consent has been obtained the patient will be given a baseline survey. This survey will then be repeated annually for the next 2 years. Three surveys in total. If the patient is chosen for the COACH intervention (see sections d.iii-v), they will also receive an additional survey post-intervention. The patient has the option of completing the survey themselves or completing it with a trained survey researcher. Clinic staff will also participate in a modified version of the survey to assess their attitudes towards HD and kidney transplantation.

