Transplant Eligibility: Previous studies have shown that not all suitable candidates are referred by their nephrologist. All patients will be evaluated via chart review by a study transplant nephrologist for transplant candidacy and, if eligible, the primary nephrologist will be asked whether the patient is an appropriate candidate and reasons they have not been referred. We will defer the transplant referral to the attending nephrologist. Our criteria for transplant ineligibility are nursing home resident, >79 years of age⁴⁷, active or recent malignancy, inoperable coronary artery disease, or comorbid illness that will make it unlikely that the patient will survive >3 years after transplant.

Recruitment Goals and Expected Survey Response (AIM 1 and AIM 2): Our goal will be to conduct a census. Our previous response rates^{1,4} have been consistently over 90%, most likely due to the non-invasive nature of the study. We anticipate recruiting 252 patients; however, we are budgeted as if all 280 patients participate.

Retention/Attrition: Based on our previous study¹, patients are amenable to repeated surveys and do not leave the HD clinic unless they transfer, are transplanted, or die. The mortality of transplant candidates is lower than the average mortality, and we are powered for an overall 2 year mortality¹⁸ of 10% and 5% transfer rate.

Participant Remuneration: Patients will receive a \$10 gift card after completing each survey.

Data Collection AIM1 and AIM2:

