Analysis: We will compare and contrast both network and nodal attributes based on sex and race/ethnicity. We will use a multivariable linear regression to test if gender and race can predict clustering coefficient while controlling for age, HD vintage and socioeconomic status. We will refine our network model by adding and removing links with each wave of the survey. For the nodal attributes that are continuous variables, standard tests of hypothesis such as t-test, ANOVA, and linear regression will be used. For categorical attributes, ANOVA density-models as well as logistic regression models will be used. For continuous variables, testing distances and similarities, Moran statistics will be calculated. Since the observations are not independent observations drawn at random from a large population, we will use a boot-strap approach for estimating the variation of estimates from a large number of random sub-samples of network members⁵⁰⁻⁵².

Limitations: Having patients self-report their own social links, while an established methodology, can still be subject to recall bias⁵¹. Thus, we will use observations of social interactions for verification using the aforementioned log. These observations will be used to weight the survey generated links.

Approach to AIM 2: Using network information from AIM 1, we will examine how structural differences in social networks affect knowledge, attitudes, and behaviors towards kidney transplantation. **H2:** Patients with dense HD social networks have similar attitudes (both positive and negative) about transplantation and completion of steps to kidney transplant as compared to patients diffuse networks.

Rationale: We have found the primary barrier to the transplant wait-list is the completion of the work-up^{1,4}. Previous research shows that patients in small dense networks share similar ideas⁴². This could either positively^{1,26} or negatively¹⁰ affect access and progress to kidney transplantation. We are using steps completed to measure progress to transplantation; a measure has been established for transplant disparity research to improve the granularity of the measurement and compare results across studies².

Step	Description
1	suitability for referral to transplant center
2	interest in transplantation
3	referral call to transplant center
4	first visit to transplant center
5	transplant center work-up
6	work-up complete
7	active on the list
8	successfully received a kidney transplant

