Analytic Plan AIM 2: To test **H2**, we will use the network information from Aim 1 to analyze correlation of knowledge, attitudes, and behaviors between members of the network (transplant discussions, living donor recruitment, and step in kidney transplant process) from the surveys and the EMR.

Primary Outcome: Correlation of 1) attitudes about transplantation and 2) step in transplant process

Independent Variables: Clustering coefficient and attributes of alters

Covariates: Age, Marital Status, HD vintage, insurance, transplant eligibility, HD clinic, network attributes

Analysis: We will examine how knowledge, attitudes, and completion of steps differ by network attributes. These differences will then be validated by using logistic regression modeling to predict patient's attitudes towards transplantation and step in the transplant work-up using demographic and survey variables. We will then add network attributes and quantify the improvement in the prediction model using tests for goodness of fit. To further validate the model we will perform an Exponential Random Graph Model (ERGM) with temporal attributes⁵³ in which the patients current transplant step is a function of patients baseline data and network attribute as well as their alters' baseline step, current step, and network attributes.

Limitations: We have previously found that patients are often incorrect about their listing status⁴, thus we will confirm the transplant status by contacting the listing institution. Using the steps completed will allow for the analysis of patients that are highly motivated who complete all their work-up but are discovered to have an absolute contraindication to transplantation. Since AIM 1 and 2 are observational, we will be unable to determine whether patients form small networks with like-minded individuals or whether over time everyone in a small network will reach a common belief through spread of information and behaviors⁵⁴. To test the spread of information and behaviors, in **AIM 3**, we will use a network targeted intervention.

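### The study's query to the primary nephrologist may itself prompt referrals, which the step outcome counts, and neither Aim 2 nor the COACH pre-post comparison can separate this from network or COACH effects

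*SAP*

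**What the plan says.** The SAP (section 3.C, Transplant Eligibility) opens with "Previous studies have shown that not all suitable candidates are referred by their nephrologist". A study transplant nephrologist then reviews all charts and, "if eligible, the primary nephrologist will be asked whether the patient is an appropriate candidate and reasons they have not been referred". Protocol section 7.b plans the same contact for eligible patients who have no referral yet: "the transplant nephrologist will discuss with the primary nephrologist if the participant is an appropriate candidate and reasons they have not been referred". Both documents leave the decision where it was; the SAP states "We will defer the transplant referral to the attending nephrologist".

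The step table under Aim 2 scores step 1 as "suitability for referral to transplant center" and step 3 as "referral call to transplant center". The Aim 2 primary outcome is "Correlation of 1) attitudes about transplantation and 2) step in transplant process", and steps completed is also a primary outcome in Aim 3. The Aim 2 analytic plan counts the step reached among the behaviors, and the Staggered Surveys paragraph of Aim 3 proposes a pre-post assessment of knowledge and behaviors. I therefore take the pre-post comparison to include steps.

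Aim 2 covariates include transplant eligibility and clinic, but not shift or nephrologist. Aims 1 and 3 do list shift. The Aim 2 Limitations paragraph begins one argument with "Since AIM 1 and 2 are observational" and weighs like-minded grouping against spread through the network. It does not mention the query.

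**The concern.** The study contacts the person who controls step 3 and asks about patients who have not reached it. Deferring the decision means that the study does not refer anyone; it does not prevent the question from prompting a referral. A prompted referral scores as progress with no network or COACH effect behind it.

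Three routes into the analyses need separate treatment.

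- **Aim 2.** The analysis correlates steps between linked patients and relates them to network attributes. If linked patients share a nephrologist or a shift, prompted referrals could arrive together and look like network influence.
- **COACH pre-post.** If the query falls between the pre and post measurements, a within-group step gain includes it. Comparison with non-COACH patients removes only part, because recipients must be eligible and many controls are not.
- **Cluster versus Central.** Both arms receive the same query, so a bias needs a difference between arms in querying or in response.

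Timing is unclear. The SAP places the review in the Aim 1-2 recruitment text, while Protocol 7.b places it beside the COACH eligibility rule. In the SAP timeline, Aim 2 follow-up runs from Year 2 Q1 to Year 3 Q4, and Wave 2 and the Aim 3 experiment both start in Year 3 Q1.

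**Working it through.** **Inputs from the SAP.** About half of 250 participants, or 125, are expected to be eligible and not listed. Two patients on each of 12 shifts receive COACH: 2 × 12 = 24. (Protocol 7.d.iv says one per shift, which gives 12.) Planning values for steps are 7 (SD 1.5) versus 5 (SD 1.7), with a stated effect size of 1.06 for 2 steps.

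**The plan's own figures.** A two-sided t-test at 0.05 with effect size 1.06 and 15 per arm has power 0.800, so the stated total of 30 reproduces. The implied SD is 2/1.06 = 1.89; the pooled SD from the stated values is √((1.5² + 1.7²)/2) = 1.60. With 60 per arm and a 1-step difference, power is 0.82 (SD 1.89) or 0.92 (SD 1.60). I use both SDs below as the SD of change, which is an assumption.

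**Assumption on the query.** The documents give neither the number unreferred nor a response rate. I assume that a fraction f = 0.10 to 0.50 of queried, unreferred patients moves one step.

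1. *Mean shift in queried, unreferred patients:* f × 1 = 0.1 to 0.5 step.

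2. *Mean shift across eligible, unlisted patients:* f × u, where u is the share not yet referred. The 125 are unlisted, not unreferred; patients at steps 3 to 6 are unlisted but already referred. For illustration, the SAP's preliminary survey had 34 of 116 patients (29%) in evaluation. If that held here and all were eligible and unlisted, 0.293 × 250 ≈ 73 of the 125 would already be referred. That leaves 52, so u = 52/125 = 0.42 and the shift is 0.04 to 0.21 step.

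3. *Within-group pre-post, no COACH effect, query between the two measurements, all recipients unreferred (worst case):* the added variance is f(1−f). The chance of a significant one-sample t-test is 6% to 29% with 24 recipients at SD 1.60 and 6% to 23% at SD 1.89. With 12 recipients it is 5% to 16% and 5% to 13%. The nominal rate is 5%.

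4. *Recipients versus all non-recipients:* with 24 recipients, the eligible and unlisted share of controls is (125 − 24)/(250 − 24) = 101/226 = 45%, so 55% of the shift in eligible patients remains in an unadjusted difference. That is 0.055 to 0.28 step if u = 1, or 0.02 to 0.12 if u = 0.42. With 12 recipients, 113/238 = 47% and 53% remains. If controls have the same eligibility and unreferred share as recipients, it cancels in expectation.

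5. *Aim 2:* a push that is independent of ties adds no correlation between linked patients of the same eligibility. In the opposite extreme, where a linked, queried, unreferred pair always responds together, the correlation added is f(1−f)/(SD² + f(1−f)). At SD 1.60 this is 0.09/2.66 = 0.03 to 0.25/2.82 = 0.09; at SD 1.89, 0.09/3.65 = 0.02 to 0.25/3.81 = 0.07. Further steps after a prompted referral would raise these figures.

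6. *Cluster versus Central:* with equal queries and responses the bias is 0. The added variance lowers power for 1 step at 60 per arm, at worst (f = 0.5, all queried and unreferred), from 0.92 to 0.90 or from 0.82 to 0.80.

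**The case against.** The strongest reply is that the effect may be small and is already partly handled. Referral stays with the attending nephrologist. The SAP's Preliminary Results report that referral is not the main barrier; completing the required tests is. Aim 2 adjusts for transplant eligibility and clinic, and its temporal network model uses patients' baseline data and alters' baseline step. No text describes how patients are divided among nephrologists, so shared response along ties is a possibility and not a documented fact. For COACH, the SAP's placement of the review suggests that the query comes about a year before the pre-COACH survey, and the plan has non-COACH controls.

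Most of this stands as a limit on size. It does not remove the mechanism: the timing is inferred from placement only, Protocol 7.b points to COACH eligibility, the controls differ from recipients in eligibility, and nephrologist and shift are absent from the Aim 2 covariates.

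A reader might also infer that step gains are in fact partly caused by the study. The documents support only that they may be: no response rate is given, and the SAP says that not all suitable candidates are referred, which is not a statement that non-referral is frequent.

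**Conclusion.** The concern holds as a possible and unmeasured source of step progress. Some progress in Aim 2 and in the within-group COACH comparison may come from the study's contact with the nephrologist. In Aim 2 this becomes bias only if response is shared along ties or differs by network position. In the pre-post analysis it matters if the query falls near COACH, or if controls include ineligible, unqueried patients.

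The size is unknown. The shift of 0.1 to 0.5 step in queried, unreferred patients, and less across all eligible patients, rests entirely on the assumed 10-50% response and one step per response.

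Two stronger readings are not supported. The shift should not be set against the 1-step difference in the SAP's power statement, because that is a Cluster-Central difference and a push common to both arms cancels from it. Nor should the assumed rates be applied to all 125 patients, since that count is of unlisted patients and the unreferred number is smaller and not given.

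The changes are cheap and worth making, because an effect not logged at the time will be hard to separate later.

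**What to change.** Amend the SAP (Transplant Eligibility and the Aim 2 and Aim 3 analysis text) and Protocol 7.b as follows.

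- Record each patient's baseline step before the query.
- Complete the review and query for all enrolled patients in the Year 2 baseline window, on one schedule for all shifts. Log the date, a nephrologist code and the outcome. Finishing merely before Wave 2 would not be enough for Aim 2, whose follow-up is already running by then.
- Take the pre-COACH step at Wave 2, after the query.
- Add nephrologist and shift to the Aim 2 step models.
- In the COACH step comparison, restrict controls to transplant-eligible patients, preferably those not already listed, to match the group from which recipients are drawn.
- Run a sensitivity analysis that counts only steps 4 and above. This removes the referral step itself, though not later steps that follow a prompted referral.
- List the query under Limitations.

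An indicator for having been queried is not recommended: it would largely duplicate eligibility (SAP wording) or baseline step (Protocol wording), and would not separate prompted from unprompted referrals. Referral decisions stay with the attending nephrologist, as written.

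The cost is that the query work is done earlier, a short log is kept, and a few degrees of freedom are used in the Aim 2 models.

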clustering coefficients were associated with completing steps and even successfully receiving a kidney transplant. This study was the first to perform a social network analysis on patient-patient interactions in an HD clinic and use it to model progression through the steps of transplantation. We hypothesize these dense networks function like echo chambers reinforcing both information and behaviors within the network. Although this study found that women were less likely to be in the network, women were unexpectedly underrepresented in this study. The proposed research will advance our understanding of sex differences in HD social networks.

B) Overview of Research Strategy

The proposed research expands on previous knowledge by combining both a longitudinal observational cohort study design (**AIMS 1 and 2**) and a clinical intervention trial (**AIM 3**) to evaluate the structure, function, and potential utilization of social networks in a racially diverse suburban clinic and compare that to a predominantly black urban clinic. The clinical trial will use a network targeted transplant education intervention (COACH) as to test the role of the network in the dissemination of knowledge, attitude, and behaviors with the overall goal of improving access to kidney transplantation (**AIM 3**).

C) Approach by AIM

Approach to AIM 1: Compare HD patient social networks by gender and race. **H1:** Female HD patients of all race and ethnicities have dense social networks when compared to white male HD patients.

Rationale: Previous social network research has shown that women and minorities tend to have dense social networks. This may contribute to gender and racial inequities in transplantation and greater insight may inform future interventions to minimize this disparity

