Setting AIM 1,2,3: This study will include ESRD patients from two independently-functioning non-profit HD clinics in North Brunswick, New Jersey and Philadelphia, Pennsylvania owned by Dialysis Clinics Incorporated (DCI) (see Medical Directors' letters). These clinics were chosen for their similar size and diverse populations existing within a centralized electronic medical record system (DARWIN) supported by DCI. The Philadelphia clinic is serves a urban, minority population, (94% African American; 1% Caucasian; 5% Hispanic patients); and a median income⁴³ of \$28,363. In contrast, DCI North Brunswick is a suburban clinic with an ethnically diverse patient population (43% White, 37% African American, 12% Asian, 8% Hispanic); a median income⁴³ of \$82,406. Each clinic has an average census of 140 patients (280 total) with 3 shifts on Monday, Wednesday, Friday (MWF) and Tuesday, Tuesday, Saturday (TTS), with approximately 25 patients per shift.

Research Staff Training and Quality Control: At the end of **Year 1**, the research coordinator (RC) and assistant (RA) will be provided reading materials on LDKT, RCTs, and receive a 6 week training in administration of the survey and conducting semi-structured interviews. They will be trained in survey administration (**Year 1**) and COACH intervention facilitation (**Year 2**). The PI will demonstrate semi-structured interview administration and then observe them complete 2 interviews and 2 interventions before they will be allowed to do so alone. The PI will oversee data coding and will provide ongoing supervision of their performance and skill development.

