Survey Instrument: The *Dialysis Patient Transplant Questionnaire* (DPTQ) includes a mix of 49 questions, single measures, and scales previously validated in HD and transplant populations and items developed to address the co-investigators' specific research interests (see appendix). The DPTQ has demonstrated construct validity in previous studies^{1,4,11,12}. It includes 17 items on communication confidence developed specifically to evaluate the COACH program and rated along a scale from 0 to 100 (Cronbach's alpha = .90); summed to create a composite confidence score. In addition, there are 12 true/false items on transplant knowledge items; correctly answered items are summed to create a composite knowledge score. The questionnaire will also include questions regarding medical conditions which may preclude the patient from transplantation. Clinic staff will also participate in a modified version of the survey to assess their attitudes towards HD^{48,49} and kidney transplantation, during Year 2.

Participant HD Seating and Observed Interaction Log: Patient seating assignments will be recorded, as well as, the staff observed social interaction log, which documents the frequency, duration, and nature of observed patient-patient interactions (appendix).

Clinical Data: Upon consent, routine HD laboratory and clinical data (including co-morbid conditions, e.g. diabetes, congestive heart failure, cardiovascular disease, chronic obstructive pulmonary disease, and malignancy, which will be reconciled with survey data) will be extracted from the DARWIN database by the DCI Information Technology Department. Data will be downloaded, cleaned, merged, and submitted for preliminary analysis. Patient's steps to transplantation (Table 2)^{1,2} will be recorded and listing status will be verified with the patient transplant center or centers (**AIM 2**).

Analytic Plan AIM1: To test **H1**, we will create nodal network graphs (Figure 1, for example) using data collected from the patient and staff surveys, and clinical observations. We will characterize and compare the structure of the patient HD clinic networks by gender and race. We will assign demographic, survey, and clinical data abstracted from the EMR to each node in the network.

Primary outcome: Differences in clustering and centrality by gender and race (**H1**)

Independent Variables: Sex and Race

Covariates: Age, Marital Status, HD vintage, insurance, HD Clinic, and HD shift

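### The SAP gives two different adjustment sets for the Aim 1 primary regression; the shorter one omits clinic, and nearly all White patients are in one clinic

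*SAP*

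**What the plan says.** H1 (SAP, Approach to AIM 1) is that "Female HD patients of all race and ethnicities have dense social networks when compared to white male HD patients". The primary outcome is "Differences in clustering and centrality by gender and race".

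Two statements of the adjustment set follow one another in the Aim 1 analytic plan:

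- The covariate line: "Covariates: Age, Marital Status, HD vintage, insurance, HD Clinic, and HD shift".
- The Analysis paragraph directly after it, which will fit a multivariable linear regression to "test if gender and race can predict clustering coefficient while controlling for age, HD vintage and socioeconomic status".

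The second drops marital status, insurance, clinic and shift. It adds SES, which is not in the list and is not defined in either document.

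The Setting section gives the race mix of the two clinics. Philadelphia is "94% African American; 1% Caucasian; 5% Hispanic patients" and North Brunswick is "43% White, 37% African American, 12% Asian, 8% Hispanic". Each has an average census of 140.

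**The concern.** Only the Analysis paragraph describes the clustering regression as a model, so an analyst could reasonably run it as worded, without clinic. White men, the H1 reference group, are almost all in one suburban clinic. Clustering is built from who interacts with whom inside a clinic, through surveys and a staff observation log, so layout or logging practice could plausibly shift it between sites. Without a clinic term, part of such a shift would be attributed to race.

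The error can go either way. A denser Philadelphia clinic would give spurious support to H1. A denser North Brunswick clinic would mask a true effect. The planned bootstrap addresses the variability of the estimates and does not remove this bias. Leaving two adjustment sets in the plan also allows the choice to be made after the data are seen.

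**Working it through.** **Plan's own figure.** Census 280 with 90% response: 280 × 0.90 = 252, the SAP's anticipated sample. The SAP states no Aim 1 effect size, power or clinic difference.

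**Race by clinic** (Setting percentages × 140):

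| | Philadelphia | North Brunswick | Share at North Brunswick |
|---|---|---|---|
| White | 1.4 | 60.2 | 60.2/61.6 = 97.7% |
| Black | 131.6 | 51.8 | 51.8/183.4 = 28.2% |
| Asian | 0 | 16.8 | 100% |
| Hispanic | 7.0 | 11.2 | 61.5% |

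**Leakage.** Let D be the clinic difference in mean clustering, with no race effect within clinic and no SES term. The bias equals the difference in clinic share times D.

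- Black-White: (0.977 − 0.282) × D = 0.695 D, about 69%.
- H1, with sex balanced within race and clinic so that women are split evenly between clinics: (0.977 − 0.50) × D = 0.477 D, about 48%.

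**False Black-White findings, no SES term.** I simulated 252 patients (126 per clinic, race mix as above) with no race effect, independent normal errors and two-sided 0.05, and fitted the regression on sex and race with and without clinic, 4,000 datasets per setting. The SDs of 0.30 and 0.35 come from the prior study under Preliminary Results. D is my assumption.

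| D | Without clinic, SD 0.35 | Without clinic, SD 0.30 | With clinic |
|---|---|---|---|
| 0.05 | 10% | 11% | about 5% |
| 0.10 | 24% | 31% | about 5% |
| 0.15 | 46% | 59% | about 5% |
| 0.20 | 72% | 82% | about 5% |

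Repeat runs at SD 0.35 gave 23-26% at D = 0.1 and 69-72% at D = 0.2.

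**With an income-based SES.** The Setting section gives median incomes of $28,363 and $82,406, so the log difference is ln(82,406/28,363) = 1.07. I took SES as log income with an assumed within-clinic SD of 0.2 to 0.8. Leakage then falls from 0.69 to about 0.1-0.55. At SD 0.35, false Black-White findings are about 4-17% for D = 0.1 and 6-45% for D = 0.2. The narrower income varies within a clinic, the better it stands in for clinic.

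**H1 contrast, no SES term.** False findings are about 9-12% at D = 0.1 and 23-30% at D = 0.2 over the two SDs, against about 5% with clinic.

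**Cost of adding clinic.** For White/Black by clinic, phi = |1.4 × 51.8 − 131.6 × 60.2| / √(133 × 112 × 61.6 × 183.4) = 0.605. The variance inflation is 1/(1 − 0.605²) = 1.58, so the standard error ratio is √1.58 = 1.26. In the simulation the standard error goes from 0.055 to 0.067 (ratio 1.22) at SD 0.35. For the pooled H1 contrast the rise is about 5-8%.

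**The case against.** The strongest reply is that the plan does include clinic and shift. The covariate line names both, it stands immediately before the Analysis paragraph, and a formal list of outcome, independent variables and covariates is where many readers would look for the adjustment set. Aim 2 follows the same layout, with a list that names clinic and looser prose after it. The Overview also commits to comparing the suburban clinic with the urban one, so a clinic difference would be looked at. This stands: a reader who sees only the regression sentence might infer that the SAP leaves clinic out of Aim 1 altogether, and it does not.

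Three further points also stand.

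- A reader might infer that race and clinic are inseparable. That is close to true for White and Asian patients, but about 52 of 183 Black patients attend North Brunswick beside about 60 White patients, so both effects can be estimated together.
- The regression sentence does adjust for SES, and an income measure would carry part of the clinic contrast. The 25% and 70% rates are therefore the no-SES extreme.
- H1 is not the Black-White contrast, and its leakage is smaller.

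What the reply does not do is reconcile the two statements. SES is undefined, so how much it absorbs is unknown, and it cannot be relied on to replace a clinic term.

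**Conclusion.** The SAP contradicts itself on the adjustment set for its Aim 1 primary regression, and the difference matters. If the regression sentence governs, up to about 69% of a clinic difference passes into the Black-White coefficient and about 48% into the H1 contrast, less the part that SES absorbs. If the covariate line governs, this bias is removed.

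It is tempting to say that a clinic difference would be reported as a race difference. The documents support only that it could be: they report no clinic difference in clustering, and they do not say which statement prevails. The error rates rest on assumed values of D, on SDs from the prior study, on independent normal errors and, for H1, on sex being balanced within race and clinic. No race-by-shift figures are given, so I make no claim about the size of any confounding by shift.

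**What to change.** Rewrite the Aim 1 regression sentence so that it adjusts for the covariates already listed: age, marital status, HD vintage, insurance, clinic and shift, with clinic and shift as fixed effects. Either define SES and add it to the list, or replace it with the listed variables. State H1 explicitly as the contrast of women with white men.

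Report the same contrast within North Brunswick as a sensitivity analysis. With about one White patient in Philadelphia, the adjusted Black-White comparison rests almost entirely on that clinic anyway. At full census, and with sex balanced, it would compare about 140/2 = 70 women with 60.2/2 = 30 white men. This analysis goes slightly beyond resolving the contradiction, but it needs no new data.

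The change is to SAP wording only, since the plan already provides for these variables. The price is some precision: a standard error about 22-26% larger for Black-White and about 5-8% larger for the pooled H1 contrast. I would class it as a cheap improvement.
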